##### ***Presence***

An observation will be considered an event if it has at least a verbatim term and is not a Grade 0 intensity event.

Grade 0 events are not included in safety analysis but are included in separate listings.

##### ***Intensity***

Intensity for unsolicited non-serious AE will be derived according to the following classification: None, Grade 1, Grade 2, Grade 3, or Missing.

If the unsolicited non-serious AE is measurable and its preferred term is part of the list of solicited reactions, then the measurement is derived based upon and following the same rule of the intensity scales defined in the protocol for that measurable injection site or systemic reaction.

Note that the intensity could be considered as “None” (not a reaction) in the analysis despite being considered a reaction by the investigator (e.g., swelling measurement  $>0$  mm but  $<25$  mm in adults).

Intensity for the other unsolicited non-serious AEs will correspond to the value reported in the electronic case report form (eCRF).

The maximum intensity corresponds to the highest intensity for a unique term.

### ***Time of onset***

Time of onset is derived from the start date of the unsolicited non-serious AE provided in the clinical database and the date of the vaccination:

Start date of the unsolicited non-serious AE – date of vaccination.

The time of onset should be considered as missing only if one or both of the dates are missing or partially missing.

The unsolicited non-serious AEs will be analyzed “Within 28 days”, which corresponds to AEs with a time of onset between 0 and 28 days after vaccination or missing. An AE with missing time of onset will be considered to have occurred just after the vaccination indicated by the visit number, so will be included in these tables.

Note: Unsolicited non-serious AE that occurred before vaccination (negative time of onset) or with a time of onset higher than defined above ( $>28$  days) will not be included in analysis, but will be listed separately.

Time of onset will be displayed as follows:

- D0-D3
- D4-D7
- D8-D14
- $\geq$ D15
- Missing

### ***Duration***

Duration is derived from the start and stop dates of the unsolicited non-serious AE provided in the clinical database:

Stop date of unsolicited non-serious AE – start date of unsolicited non-serious AE + 1

The duration should be considered as missing only if one or both of the start and stop dates of the unsolicited non-serious AE is missing or partially missing.

Duration will be displayed by period as following:

- 1-3 days
- 4-7 days
- 8-14 days
- $\geq 15$  days
- Missing

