Visit 2 (28 days [+7 days] after Visit 1): Collection of Safety Information and Blood Sample

1. Collect and review the diary card since V01, including any solicited reactions and AEs, medications, or therapy that occurred since vaccination. The occurrence of any injection site reaction, systemic event/reaction, any SAE, and/or any AESI should have been reported in the diary card.

Note: The assessor (Investigator/Sub-investigator who was not the administrator of the vaccine at V01) assesses the safety events.

2. Draw approximately 10 mL blood sample.

Note: If the attempts to collect blood are unsuccessful (3 attempts), the subject should be given the opportunity to return to the study site for another attempt within the visit window. If a blood sample cannot be obtained, the reason will be recorded in the blood sampling page of the CRB.

3. Contact the IRT to inform the subject's status.
4. Complete the relevant CRFs for this visit and the study termination record.

Follow-up of subjects with Related AEs or with AEs That Led to Study/Vaccination Discontinuation:

Unless a subject refuses further contact, each subject who experiences an AE (whether serious or non-serious) during the study must be followed until the condition resolves, becomes stable, or becomes chronic (even after the end of the subject's participation in the study) if *either* of the following is true:

- The AE is considered by the Investigator to be related to the product administered.
- The AE caused the discontinuation of the subject from the study.

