9.2.2.3.3 Unsolicited Adverse Events

In addition to recording solicited reactions, subjects will be instructed to record any other medical events that may occur during the 28-day period after vaccination. Space will be provided in the diary card for this purpose. Information on SAEs will be collected and assessed throughout the study, from inclusion until 28 days (+ 7 days) after vaccination. Any SAE occurring at any time during the study will be reported by the Investigator in the CRB according to the completion instructions provided by the Sponsor; this includes checking the “Serious” box on the AE CRF and completing the appropriate Safety Complementary Information CRFs. All information concerning the SAE is to be reported either as part of the initial reporting or during follow-up reporting if relevant information became available later (e.g., outcome, medical history, results of investigations, copy of hospitalization reports). See [Section 10](#) for further details on SAE reporting.

For each unsolicited AE (whether serious or non-serious), the following information is to be recorded:

- Start and stop dates¹¹
- Intensity of the event:

For measurable unsolicited AEs that are part of the list of solicited reactions, the size of the AE as well as the temperature for fever will be collected and analyzed based on the corresponding scale used for solicited reactions (see [Table 1](#) and [Table 2](#)).

All other unsolicited AEs will be classified according to the following intensity scale:

- Grade 1: A type of AE that is usually transient and may require only minimal treatment or therapeutic intervention. The event does not generally interfere with usual activities of daily living.
- Grade 2: A type of AE that is usually alleviated with additional therapeutic intervention. The event interferes with usual activities of daily living, causing

¹¹ The stop date of all related AEs will be actively solicited. For other events, the investigator will provide the stop date when it becomes available. AEs for which no stop date was obtained during the course of the study will be considered as ongoing at the end of the study.

discomfort but poses no significant or permanent risk of harm to the research participant.

- Grade 3: A type of AE that interrupts usual activities of daily living, or significantly affects clinical status, or may require intensive therapeutic intervention.
- Whether the AE was related to the IP (for unsolicited systemic AEs)

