***Overall number of days of occurrence***

If a reaction is ongoing at the end of the solicited period, then the overall number of days of occurrence is derived from the daily intensities and the stop date of the reaction after the end of the solicited period. The overall number of days of occurrence is:

$$\begin{aligned} & (\text{stop date} - \text{vaccination date}) \\ & + (\text{number of days of occurrence within the solicited period}) \\ & - \text{length of the solicited period} + 1 \end{aligned}$$

If the stop date is missing or incomplete (containing missing data [MD]), the overall number of days of occurrence will be considered as Missing.

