## ***Start Date and Stop Date***

Missing or partial missing start dates for unsolicited AEs will remain missing and not be imputed. If either the start or stop date is missing or partially missing, the time of onset will be considered to be missing. Nevertheless unsolicited AEs with missing time of onset will be included in analyses according to the visit collected.

Missing or partially missing stop dates for AEs (solicited reactions and unsolicited AEs) will remain missing and not be imputed.

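### Events with no stop date are tabulated as duration Missing even when they are known to be ongoing, so some events known to be long sit with unknown dates and displayed durations shift downward (descriptive safety tables only)

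*SAP*

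**What the plan says.** SAP 5.4.2.2 (Duration) defines the duration of an unsolicited non-serious AE as "Stop date of unsolicited non-serious AE – start date of unsolicited non-serious AE + 1". It adds: "The duration should be considered as missing only if one or both of the start and stop dates of the unsolicited non-serious AE is missing"; a partial date is treated the same way. The display rows are 1-3, 4-7, 8-14 and ≥15 days, and Missing. SAP 5.4.2.3 applies the same method to SAEs, although the SAE summaries listed in SAP 4.7.2 do not include a duration table.

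For a solicited reaction still ongoing after D7, SAP 5.4.2.1 says that if the stop date is absent or incomplete, "the overall number of days of occurrence will be considered as Missing". Table 11 has rows for 1-3, 4-7 and ≥8 days, and Missing.

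SAP 5.4.4.1 closes off any other route: "Missing or partially missing stop dates for AEs (solicited reactions and unsolicited AEs) will remain missing and not be imputed".

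The footnote on stop dates in protocol 9.2.2.3.3 gives an absent stop date a meaning: "AEs for which no stop date was obtained during the course of the study will be considered as ongoing at the end of the study". It also sets two levels of effort in obtaining the date. For related events, "The stop date of all related AEs will be actively solicited". Otherwise, "For other events, the investigator will provide the stop date when it becomes available".

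**The concern.** An event known to be unresolved at the last visit does not have an unknown duration. It has a lower bound, and often that bound already places it in the top category. The SAP discards that information and puts the event in the same row as one whose dates were never recorded.

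The loss is not neutral. For a given onset day, the longer an event lasts, the more likely it is to have no stop date. The ≥15-day and ≥8-day rows are therefore the ones that lose events. Duration of unsolicited AEs is a named secondary safety endpoint (protocol 9.2.2.2). If one vaccine produced more long-lasting events, part of that excess would appear under Missing, where a reader could not tell it from poor date recording.

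The two levels of stop-date effort also mean that durations of related and unrelated AEs could differ partly because of how the dates were collected.

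**Working it through.** The plan gives no figure for AE duration, so there is none to reproduce. The check applies the SAP's own formulas to an event that has no stop date and is ongoing at V02.

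**Inputs**
- V02 falls on D28 to D35 (protocol, Table of Study Procedures).
- Unsolicited duration = stop − start + 1 (SAP 5.4.2.2).
- Overall days of a solicited reaction = (stop − vaccination) + days within the solicited period − length of that period + 1 (SAP 5.4.2.1). The period D0-D7 is 8 days long.
- The SAP counts a solicited reaction as ongoing only if D7 is at least Grade 1, so there is at least 1 day within the period.

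**1. Unsolicited AE, onset day s, ongoing at V02 on day v.** The minimum duration is v − s + 1.
- V02 on D28: 29 − s ≥ 15 gives s ≤ 14.
- V02 on D35: 36 − s ≥ 15 gives s ≤ 21.
- Example: onset D5, ongoing at D28, gives 28 − 5 + 1 = 24 days. The SAP row is Missing; the event belongs in ≥15 days.
- With V02 on D28, onsets on D15 to D28 have known minimums of only 14 down to 1 day. Their category is not settled.

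**2. Solicited reaction unresolved at day v.** The minimum is v + 1 − 8 + 1.
- V02 on D28: 28 + 1 − 8 + 1 = 22 days. V02 on D35: 29 days. Either belongs in ≥8 days of Table 11.
- For a subject whose last contact is earlier, v + 1 − 8 + 1 ≥ 8 requires v ≥ 14.

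**3. Effect on the table (illustration, all inputs assumed).** Take 100 AEs split 60/20/10/10 over 1-3, 4-7, 8-14 and ≥15 days, and let a share of the last group lack a stop date. SAP 5.4.4 leaves missing data out of percentages unless otherwise specified, so both denominators are shown.

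| Share of ≥15-day AEs with no stop date | ≥15 row, of all AEs | ≥15 row, Missing excluded | 1-3 row, Missing excluded |
|---|---|---|---|
| 0% | 10% | 10% | 60% |
| 25% | 7.5% | 7.5/97.5 = 7.7% | 60/97.5 = 61.5% |
| 50% | 5% | 5/95 = 5.3% | 60/95 = 63.2% |
| 100% | 0% | 0% | 60/90 = 66.7% |

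The top row falls under either denominator. The short rows rise only if Missing is excluded.

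**4. Upper case (simulation, all inputs assumed).** Onset is uniform over D0-D28, V02 is uniform over D28-D35, durations are exponential, and no event gets a stop date after V02. At a mean of 10 days, 22% of AEs become Missing and 64% of those lasting ≥15 days are lost from their row. That row shows 9% of AEs, against 25% in truth and 16% with the fix. The lost share is 51% at a mean of 5 days and 77% at 20 days.

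**The case against.** The strongest reply is that the protocol already seeks the dates that matter. Stop dates of related AEs are actively sought. Protocol 5.1.4 and 9.2.2.3.5 continue follow-up of related AEs past study end until the event resolves, stabilises or becomes chronic. Solicited reactions are related by definition (protocol 9.2.2.1). The SAP takes the stop date from the database with no cut-off at V02. The protocol footnote sits under unsolicited AEs and gives a status, not a duration. Protocol 12.3.1 rules out replacing missing safety data, and Missing is a printed row, so nothing is hidden.

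Most of this stands, and it limits the scope. Three stronger readings that a reader might infer are not supported:

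- *Every event ongoing at study end becomes Missing.* Many related and solicited events should later acquire a stop date.
- *Only the longest events move.* Late-onset AEs that are ongoing at V02 may be short. In the simulation above, 30% of the Missing events at a mean of 10 days do not last 15 days.
- *About 64% of long AEs will be lost.* That figure assumes no stop date after V02 for any event, which conflicts with the follow-up rules for related AEs. Part of the loss also comes from the short follow-up: the fix recovers only about 43% of the lost long AEs in that scenario.

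The reply does not remove the point. Unrelated AEs get a stop date only when one becomes available. Related events that become stable or chronic may never get one. A rule against replacing missing values does not prevent an ongoing category or the use of a bound that the recorded dates already prove.

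**Conclusion.** Wrong as written, with low consequence. Under the SAP rule, some events that are provably ≥15 days (unsolicited) or ≥8 days (solicited) are placed under Missing, and the displayed durations shift downward.

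The events mainly affected are unsolicited AEs judged unrelated. To these are added related or solicited events that become stable or chronic, are unresolved at database lock, or occur in subjects lost to follow-up.

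The size cannot be determined from the documents, because they do not give the share of events without a stop date. The simulated 22% and 64% are an assumed upper case for missing stop dates, not an estimate for this trial.

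Table 10, which counts days from daily intensities within D0-D7, is unaffected. So are occurrence, intensity and relatedness, and the counts of SAEs and AESIs. The safety analysis is descriptive with no testing (SAP 4.7), and no primary conclusion depends on it.

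**What to change.** In SAP 5.4.2.1 and 5.4.2.2, for an event with no stop date that is recorded as ongoing at V02 or termination:

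1. Compute the minimum duration by the existing formula, with the last contact date in place of the stop date.
2. Assign ≥8 days (solicited, Table 11) or ≥15 days (unsolicited) where that minimum reaches the category.
3. Otherwise count the event in a new row for events ongoing at study end.
4. Keep Missing for unknown or partial dates.
5. State whether Missing is in the percentage denominator of these tables.

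Reconcile one related inconsistency in the same edit. SAP 5.4.4.1 makes time of onset missing when only the stop date is missing, whereas SAP 5.4.2.2 needs only the start and vaccination dates. Read literally, the former would also remove an ongoing AE from its onset category.

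The cost is a few SAP sentences and a small change to the derivation. The visit and termination dates are already used for subject duration in SAP 5.4.1, and no new data are needed.

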#### **5.4.2.3 SAEs**

##### ***Time of onset***

Time of onset will be computed using the same methodology than for unsolicited non-serious AEs described in [Section 5.4.2.2](#).

SAEs will be analyzed throughout the study using the following periods:

- Within 28 days after vaccine injection
- During the study (i.e., all SAEs occurred during the study)

An SAE with missing time of onset will be considered to have occurred just after the vaccination indicated by the visit number, and will be included in these tables.

Note: SAEs that occurred before vaccination (negative time of onset) will not be included in analysis but will be listed separately.

##### ***Duration***

Duration will be computed using the same methodology than for unsolicited non-serious AEs described in [Section 5.4.2.2](#).

##### ***Intensity***

The intensity for SAE will be computed using the same methodology than for unsolicited non-serious AEs described in [Section 5.4.2.2](#).

#### **5.4.2.4 Other Safety Endpoints**

##### ***Action taken***

This information will be summarized as collected, including missing observation. No derivation or imputation will be done.

### ***Seriousness***

This information will be summarized as collected for SAE. No derivation or imputation will be done.

### ***Outcome***

This information will be summarized as collected. No derivation or imputation will be done.

### ***Causality***

This information will be summarized as collected. An adverse reaction (AR) is defined as an unsolicited non-serious AE or an SAE with causality to the vaccine. Missing causality (relationship) will be handled as described in [Section 5.4.4](#).

### ***AEs leading to study discontinuation***

A flag is available in the clinical database for all AEs in order to identify AEs leading to discontinuation.

In general, the items that are counted are:

- Disposition table: A subject who has, on the termination form, the reason for early termination “Adverse Event” is checked.
- Safety overview table: A subject who has either on the termination form, the reason for early termination “Adverse Event” is checked or lists an AE on an AE page (solicited, unsolicited, or SAE) that has “Caused Study Termination” checked that is at least Grade 1 and is within the time period indicated. Note: If the Grade is below 1, the AE will be excluded from the list of AEs leading to study discontinuation.
- System organ class (SOC)/Preferred term (PT) table: An event (solicited, unsolicited, or SAE) that has “Cause Study Termination” checked that is at least Grade 1 and is within the time period indicated.

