### ***Causality***

Missing causality (relationship) for unsolicited non-serious AEs and SAEs will be considered at the time of analyses as related to vaccination.

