## ***Intensity***

For solicited reactions, missing intensities will be handled as described in “Daily intensity” of [Section 5.4.2.1](#). For unsolicited non-serious AEs, missing intensities will remain missing and will not be imputed.

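### Does the Grade 1 minimum for AEs leading to discontinuation wrongly drop a flagged event that has no recorded grade?

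*SAP*

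**What the plan says.** SAP 5.4.2.4, under AEs leading to study discontinuation, sets counting rules for three outputs:

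- **Disposition table:** "A subject who has, on the termination form, the reason for early termination" marked as an adverse event. Grade plays no part.
- **Safety overview:** a subject counts either through that form or through an AE page whose study-termination box is "checked that is at least Grade 1 and is within the time period indicated". A note in the same bullet adds: "If the Grade is below 1, the AE will be excluded from the list of AEs leading to study discontinuation".
- **SOC/PT table** (listed in SAP Table 6, within 28 days): the AE-page flag only, with the same grade and period condition.

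The presence rule in SAP 5.4.2.2 is worded differently: "An observation will be considered an event if it has at least a verbatim term and is not a Grade 0 intensity event". That subsection is limited to unsolicited non-serious AEs. It allows five intensity values: None, Grades 1 to 3, and Missing as a category of its own. SAP 5.4.4.1 adds: "For unsolicited non-serious AEs, missing intensities will remain missing and will not be imputed".

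**The concern.** The SAP itself provides for a missing grade, yet SAP 5.4.2.4 never mentions one. Such an event does not reach Grade 1, and it is not stated to be below Grade 1 either. The minimum and the note therefore seem to point in different directions, and the presence rule counts the event.

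The SAP also tends to keep events when other fields are blank. For onset, "An AE with missing time of onset will be considered to have occurred just after the vaccination indicated by the visit number". For relationship, "Missing causality (relationship) for unsolicited non-serious AEs and SAEs will be considered at the time of analyses as related to vaccination". Dropping an event because its grade is blank looks out of line with both.

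At stake is the SOC/PT description of why a subject left the study. A subject could be counted as discontinued for an AE while the table that should name the AE shows nothing.

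**Working it through.** No figure in the plan is in dispute, so the check is a comparison of rules.

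**1. Each intensity value.** Take a flagged, in-period unsolicited non-serious AE with a verbatim term:

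| Intensity | Presence rule (5.4.2.2) | Grade 1 minimum (5.4.2.4) | Below-1 note (5.4.2.4) |
|---|---|---|---|
| None / Grade 0 | not an event | not met | excluded |
| Grade 1, 2 or 3 | event | met | not excluded |
| Missing | event | not met | not triggered |

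The rules part company on Missing only, one value of five.

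**2. Whether the text gives an answer.** It does. SAP 5.4.4.1 leaves the grade missing, and a missing grade cannot satisfy a minimum of Grade 1, so the event is left out of the SOC/PT table. The note sits in the overview bullet, not the SOC/PT bullet. It reads as a gloss on the minimum, for cases such as a swelling under 25 mm that is derived as None (SAP 5.4.2.1 and 5.4.2.2). Excluding grades below 1 does not amount to including ungraded events.

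**3. Event types.**
- *Unsolicited non-serious AEs:* the mismatch in step 1 applies.
- *Solicited reactions:* no contrast. SAP 5.4.2.1 already leaves out a subject with no non-missing presence for that endpoint.
- *SAEs:* SAP 5.4.2.3 borrows the onset, duration and intensity rules from 5.4.2.2 but not the presence rule. Its reference to all SAEs during the study defines an analysis period. An ungraded flagged SAE would fail the Grade 1 minimum and would presumably still appear in the SAE tables, but only because nothing there mentions grade.

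The firm conflict is thus in one event type of three. A second rests on silence.

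**4. Other missing-field rules.** Practice is not uniform. Under the Immediate heading of SAP 5.4.4.1, a non-serious systemic AE with that field blank is taken as later than the 30-minute period, and an SAE with missing elapsed time is not treated as immediate. Both stay in the general tables and leave the special category because a qualifying field is blank. SAP 5.4.4 also leaves missing categorical data out of percentages by default. Omitting an ungraded event from a grade-conditioned table fits that pattern.

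**5. What would be lost.** The subject count is generally kept. Protocol 5.2.8 has the investigator record a safety-driven withdrawal as an adverse event, and Protocol 5.2.10 ranks that reason first. The form then puts the subject in the disposition and overview tables whatever the grade. Listings must show missing data as missing (SAP 5.4.4.1). Only the SOC/PT line for that event is at risk.

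**6. How many.** Protocol 9.2.2.3.3 requires intensity for every unsolicited AE, serious or not. Protocol 5.1.4 requires follow-up of any AE that caused discontinuation, unless the subject refuses contact. Missing information must be explained (Protocol 11.1) and queries completed before lock (Protocol 13.4.1). For scale, the planning assumption of 5% attrition allows 0.05 × 2100 = 105 subjects to be lost to the FAS for all reasons. Discontinuations for an AE would be some part of such losses, and ungraded ones a part of that part. The documents give no count for either.

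**The case for a change.** The best case for a change is this. Whether an event led to early termination is a stated secondary safety endpoint for unsolicited AEs and for SAEs (Protocol 9.2.2.2). For SAEs that endpoint does not list intensity, yet grade decides whether the SAE that ended participation is shown in the SOC/PT table. The omission is nowhere spelled out, and a reader comparing the overview with the SOC/PT table could meet an unexplained gap. One sentence would settle it, with no new data.

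Part of this stands. The wording of 5.4.2.4 and 5.4.2.2 does differ for a missing grade, and an explicit sentence would be tidier.

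The rest is weaker. The overview and SOC/PT tables can differ in any case, because one also accepts the termination form and the other uses only the flag. The edit is not confined to one table either: the Grade 1 minimum stands in both bullets. Changing both could alter the overview count for a subject identified only by the flag, and changing one would leave the two bullets inconsistent.

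**Conclusion.** The point does not call for a change. The plan has a narrow mismatch of wording, its literal reading gives a workable rule, and the likely number of affected records is zero or close to it. The subject-level discontinuation count is generally preserved. No immunogenicity result is touched, and safety is descriptive with no testing (SAP 4.7).

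This rests on two assumptions: that intensity is collected and queried as the protocol requires, and that the termination form is completed as Protocol 5.2.8 and 5.2.10 direct. If the blind data review (Protocol 11.3) did turn up a flagged event without a grade, a footnote to the table would deal with it.
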